7.2. Exclusion Criteria

Patients will be excluded from the study if they meet **any** of the following criteria:

- [13] are currently receiving an investigational drug in a clinical trial or participating in any other type of medical research judged not to be scientifically or medically compatible with this study. If a patient is currently enrolled in a clinical trial involving non-approved use of a device, then agreement with the investigator and Lilly clinical research physician (CRP) is required to establish eligibility.
- [14] have visceral crisis, lymphangitic spread, or leptomeningeal carcinomatosis. Visceral crisis is not the mere presence of visceral metastases but implies severe organ dysfunction as assessed by symptoms and signs, laboratory studies, and rapid progression of the disease.
- [15] have clinical evidence or history of central nervous system metastasis. Screening is not required for enrollment.
- [16] have received prior treatment with chemotherapy (except for neoadjuvant/ adjuvant chemotherapy), fulvestrant, everolimus, or any CDK4 and CDK6 inhibitor
- [17] have received treatment with a drug that has not received regulatory approval for any indication within 14 or 21 days prior to randomization of study drug for a nonmyelosuppressive or myelosuppressive agent, respectively
- [18] have received recent (within 28 days prior to randomization) yellow fever vaccination
- [19] have had major surgery within 14 days prior to randomization of study drug to allow for post-operative healing of the surgical wound and site(s).
- [20] have a personal history within the last 12 months of any of the following conditions: syncope of cardiovascular etiology, ventricular tachycardia, ventricular fibrillation, or sudden cardiac arrest
- [21] have serious preexisting medical conditions that, in the judgment of the investigator, would preclude participation in this study (for example, history of major surgical resection involving the stomach or small bowel)

- [22] have inflammatory breast cancer or a history of any other cancer (except nonmelanoma skin cancer or carcinoma in-situ of the cervix), unless in complete remission with no therapy for a minimum of 3 years
- [23] have received an autologous or allogeneic stem-cell transplant
- [24] have active bacterial or fungal infection, or detectable viral infection (for example, human immunodeficiency virus [HIV] or viral hepatitis). Screening is not required for enrollment.
- [25] are pregnant or breastfeeding
- [26] have initiated bisphosphonates or approved RANK ligand (RANK-L) targeted agents (for example, denosumab) <7 days prior to randomization

7.3. Discontinuations

7.3.1. *Discontinuation of Patients*

The criteria for enrollment must be followed explicitly. If the investigator site identifies a patient who did not meet enrollment criteria and who was inadvertently enrolled, the sponsor must be notified. If the sponsor identifies a patient who did not meet enrollment criteria and who was inadvertently enrolled, the investigator site will be notified. A discussion must occur between the sponsor CRP and the investigator to determine whether the patient may continue in the study, with or without study drug. Inadvertently enrolled patients may be maintained in the study and on study drug when the Lilly CRP agrees with the investigator that it is medically appropriate for that patient. The patient may not continue in the study with or without study drug if the Lilly CRP does not agree with the investigator's determination that it is medically appropriate for the patient to continue. The investigator must obtain documented approval from the Lilly CRP to allow the inadvertently enrolled patient to continue in the study with or without study drug.

In addition, patients will be discontinued from the study drug(s) and/or from the study in the following circumstances:

- Progressive disease (PD) as defined by RECIST v1.1.
- enrollment in any other clinical trial involving an investigational product or enrollment in any other type of medical research judged not to be scientifically or medically compatible with this study
- investigator decision
 - the investigator decides that the patient should be discontinued from the study or study drugs
 - if the patient, for any reason, requires treatment with another therapeutic agent that has been demonstrated to be effective for treatment of the study indication, discontinuation from the study drugs occurs prior to introduction of the new agent
- patient decision
 - the patient or the patient's designee (for example, parents or legal guardian) requests to be withdrawn from the study or study drug
- sponsor decision

- Lilly stops the study or stops the patient's participation in the study for medical, safety, regulatory, or other reasons consistent with applicable laws, regulations, and good clinical practice (GCP)

The reason and date for discontinuation will be collected for all patients. All randomized patients who discontinue regardless of whether or not they received study drug will have procedures performed as shown in the Study Schedule ([Attachment 1](#)).

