Informed consent	A process by which a patient voluntarily confirms his or her willingness to participate in a particular trial, after having been informed of all aspects of the trial that are relevant to the patient's decision to participate. Informed consent is documented by means of a written, signed, and dated informed consent form.
interim analysis	An interim analysis is an analysis of clinical trial data, separated into treatment groups, that is conducted before the final reporting database is created/locked.
investigational product	A pharmaceutical form of an active ingredient or placebo being tested or used as a reference in a clinical trial.
investigator	A person responsible for the conduct of the clinical trial at a trial site. If a trial is conducted by a team of individuals at a trial site, the investigator is the responsible leader of the team and may be called the principal investigator.
ITT	intention-to-treat The principle that asserts that the effect of a treatment policy can be best assessed by evaluating on the basis of the intention to treat a patient (that is, the planned treatment regimen) rather than the actual treatment given. It has the consequence that patients allocated to a treatment group should be followed up, assessed, and analyzed as members of that group irrespective of their compliance to the planned course of treatment.
IWRS	interactive web response system
legal representative	An individual, judicial, or other body authorized under applicable law to consent on behalf of a prospective patient to the patient's participation in the clinical study.

Lilly Safety System	Global safety database that tracks and reports serious adverse and spontaneous events occurring while using a drug/drug delivery system.
LLT	Lower Level Term
MATE	multidrug and toxin extrusion protein
MedDRA	Medical Dictionary for Regulatory Activities
MRI	magnetic resonance imaging
NCI	National Cancer Institute
OS	overall survival
patient	A study participant who has the disease or condition for which the investigational product is targeted.
PD	progressive disease
PET	positron emission tomography
PFS	progression-free survival
PgR	progesterone receptor
PR	partial response
PRO/ePRO	patient-reported outcome/electronic patient-reported outcome
PS	performance status
PT	Preferred Term
randomize	the process of assigning patients to an experimental group on a random basis
RECIST	Response Evaluation Criteria in Solid Tumors

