8.1. Summary of Study Design

Study I3Y-MC-JPBL (JPBL) is a multicenter, randomized, double-blind, Phase 3 trial for women with HR+, HER2- locally advanced or metastatic breast cancer. [Figure JPBL.8.1](#) illustrates the study design.

Abbreviations: HR+ = hormone receptor positive; HER2- = human epidermal growth factor receptor 2 negative; N = number; PD = progressive disease.

Figure JPBL.8.1. Illustration of study design.

Approximately 630 EP patients will be randomized 2:1 between the 2 arms:

- Experimental Arm A: abemaciclib 150 mg orally Q12H on Days 1 to 28 of a 28-day cycle plus fulvestrant 500 mg intramuscularly on Days 1 and 15 of Cycle 1, then on Day 1 of Cycle 2 and beyond
- Control (Placebo) Arm B: Placebo orally Q12H on Days 1 to 28 of a 28-day cycle plus fulvestrant 500 mg intramuscularly on Days 1 and 15 of Cycle 1, then on Day 1 of Cycle 2 and beyond

Enrollment will close when approximately 450 EP patients have been randomized at a starting dose of 150 mg Q12H. Patients will be randomized using the following stratification factors: nature of disease (visceral metastases versus bone only metastases versus other) and sensitivity to endocrine therapy (primary resistance versus secondary resistance). The presence of visceral metastases refers to lung, liver, pleural, or peritoneal involvement at the time of randomization. Primary clinical resistance to endocrine therapy is defined as follows: 1) for endocrine therapy in the adjuvant setting, recurrence within the first 2 years of adjuvant endocrine therapy while on endocrine therapy or 2) for endocrine therapy in the locally advanced or metastatic setting, progression within first 6 months of initiating first-line endocrine therapy while on endocrine therapy. Patients receiving prior endocrine therapy who do not meet the definition of primary clinical resistance will be considered to have secondary clinical resistance.

Data base lock for the interim analysis for efficacy will occur when approximately 265 investigator-assessed PFS events have been observed. Database lock for the final analysis of the PFS endpoint will occur when approximately 378 investigator-assessed PFS events have been observed. All patients will be followed for progression and survival information until death or study completion, whichever occurs first.

Details on sample size and analysis in Sections 12.1 and 12.2.

Terms used to describe the periods during the study are defined below:

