10.1.2. Efficacy Assessments during the Study Period Postdiscontinuation Follow-Up

Postdiscontinuation follow-up during the study period will be conducted as described in the Study Schedule ([Attachment 1](#)).

For those patients who are randomized and never receive study treatment or those who discontinue study treatment without objectively measured PD, the investigative sites will continue to monitor patients and periodically evaluate tumor response approximately every 8 weeks for the first 12 months following randomization and thereafter approximately every 12 weeks by the same method used at baseline and throughout the study until the patient has objective disease progression, or until the final analysis of PFS. After the patient has objective disease progression, radiologic tests are no longer required and the patient will be followed up approximately every 12 weeks (\pm 14 days) until the patient's death or overall study completion.

Lilly will continue to collect survival data on all patients but may reduce data collection for other efficacy data. Lilly will notify investigators when this reduced data collection can begin.

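### Section 7.3.1 can be read as ending progression and survival follow-up for randomized patients later found ineligible, in conflict with the protocol's own follow-up rules

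*Protocol*

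**What the plan says.** Protocol Section 7.3.1 covers patients who were enrolled although they did not meet the criteria. The investigator and the sponsor physician discuss whether the patient may go on. If they disagree, "The patient may not continue in the study with or without study drug if the Lilly CRP does not agree" with the investigator's view. The closing sentence of that paragraph requires documented sponsor approval even for staying in the study without study drug.

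Three other places point the other way:

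- Section 7.3.1, after the list of discontinuation reasons and with a pointer to Attachment 1: "All randomized patients who discontinue regardless of whether or not they received study drug will have procedures performed as shown in the Study Schedule".
- Section 8.1: "All patients will be followed for progression and survival information until death or study completion, whichever occurs first".
- Section 10.1.2 continues tumor evaluation "For those patients who are randomized and never receive study treatment or those who discontinue study treatment without objectively measured PD", follows patients after progression about every 12 weeks until death or study completion, and states that survival data will still be collected on all patients.

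Section 12.2.1 defines the ITT population as all patients randomized in the EP strata per IWRS, with no exclusion for ineligibility or removal.

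**The concern.** An ineligible patient who has been randomized counts in the primary analysis whether or not she is followed. If a site takes the quoted sentence at its word, it closes her record, and her later progression and death are never seen. The reason for the missing outcome would be a medical judgment made after randomization, at any time, and possibly related to how she is doing. PFS is the primary endpoint and OS the important secondary one. Both analyses assume that censoring is unrelated to prognosis within arm, and nothing in the design requires this loss.

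**Working it through.** **1. Are these patients randomized?** Yes. Section 4 defines enrolling as assigning a patient to a treatment. An inadvertently enrolled patient has therefore been randomized and, if in an EP stratum, belongs to the ITT population (Section 12.2.1).

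**2. Does leaving the study mean leaving follow-up?** On the protocol's own usage, yes. Section 8.1 places postdiscontinuation follow-up, short- and long-term, inside the Study Period. The last row of Table JPBL.10.3 describes a patient no longer participating as one who is off study therapy and also out of follow-up. The quoted sentence separates study from study drug, so study cannot be shorthand for drug here.

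**3. Which text prevails?** Nothing says. Section 7.3.1 bars this patient from the study and, further down, orders Study Schedule procedures for every randomized patient who discontinues. Sections 8.1 and 10.1.2 agree with the second rule. Where the protocol wants follow-up to continue after an irregular event it can say so directly: Section 9.5.2 sends unblinded patients to postdiscontinuation follow-up.

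**4. What happens in the analysis if follow-up stops?**

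- PFS, Table JPBL.12.1: no post-baseline scan means censoring at randomization (Rule 2); otherwise censoring at the last adequate assessment (Rule 3). Rule 4 names only loss to follow-up and withdrawal of consent, so removal by the sponsor has no rule of its own.
- OS, Protocol Section 10.1.4 and SAP Addendum Section 4.2: censoring at last contact.

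**5. How large could it be?** First, the plan's own power figure. Inputs from Section 12.1: 378 PFS events, hazard ratio 0.703, 2:1 allocation, one-sided alpha 0.025. By Schoenfeld's formula,

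power = Φ(√(D × 2/3 × 1/3) × |ln HR| − 1.960) = Φ(√84 × 0.3524 − 1.960) = Φ(1.270) = 89.8%,

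which agrees with the stated figure of about 90%.

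The documents give no removal rate. As an assumption, take a fraction p of the 630 patients removed with no further outcomes. Lost PFS events are 378p and lost deaths are 441p. Power is recomputed with 378(1 − p) events, as if none were replaced. The last column is 441 / (630(1 − p)).

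| p (assumed) | Patients | PFS events lost | PFS power | Deaths lost | Share of the rest who must die to reach 441 |
|---|---|---|---|---|---|
| 0 | 0 | 0 | 89.8% | 0 | 70.0% |
| 1% | 6 | 3.8 | 89.5% | 4.4 | 70.7% |
| 3% | 19 | 11.3 | 88.9% | 13.2 | 72.2% |

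Both analyses are triggered by event counts, so the more likely effect is a slightly later analysis with power unchanged. What the table cannot show is bias: that depends on why these patients were removed, and the documents give nothing from which to estimate it.

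**The case against.** The best defense is that Section 7.3.1 cures itself. Its sentence on Study Schedule procedures covers every randomized patient who discontinues, and Section 10.1.2 adds survival data on all patients. A site reading the whole section would see this. That makes loss of outcomes a possibility and not a certainty, but it leaves two instructions in one section that cannot both be followed for this patient.

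Blinding also counts. Sites and the sponsor study team have no immediate access to assignments (Sections 8.2 and 9.5), and deaths and SAEs are reviewed blinded (Section 10.3.3). This guards against deliberate removal by arm. It does not stop removal from depending on the patient's condition, and Section 9.5.3 accepts that signs and symptoms can reveal treatment.

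Two stronger readings are tempting, and the documents do not support them.

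- A reader might infer that the list introduced by "patients will be discontinued from the study drug(s) and/or from the study in the following circumstances" takes patients out of survival follow-up when they enter another trial, so that many would be censored for OS. Progressive disease is on the same list, and Section 10.1.2 and Attachment 1 plainly keep progressed patients under survival follow-up. Sections 8.1.2 and 9.4 use the list as reasons to stop study drug. The phrase permits and does not require leaving the study, and no text withdraws a patient already in long-term follow-up.
- A reader might infer that the ITT analysis is broken. The analysis set is intact; only follow-up is in question. The glossary says "patients allocated to a treatment group should be followed up, assessed, and analyzed as members of that group irrespective of their compliance", but that clause concerns compliance with the planned treatment, and ineligibility is not noncompliance. The point therefore rests on the follow-up rules and not on that definition.

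**Conclusion.** The point holds for one narrow group: randomized patients later found ineligible, where the sponsor physician does not agree that they should continue. For them one sentence of Section 7.3.1 conflicts with a later sentence of that section and with Sections 8.1 and 10.1.2. A literal reading would censor them for both PFS and OS while they remain in the ITT population.

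The size is probably small. The 6 to 19 patients rest on an assumed 1% to 3%, and the effect on power is negligible. No stated sample-size or power figure is wrong. The reason to act is that the censoring is avoidable and may be informative; its direction and size cannot be known from the documents.

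**What to change.** Reconcile the sentence in Section 7.3.1 with the later text of that section and with Sections 8.1 and 10.1.2. State that a sponsor decision against continuation of an ineligible randomized patient does not end progression and survival follow-up, and that this continues under the postdiscontinuation schedule in Attachment 1 unless the patient withdraws consent to follow-up. Leave the decision on who stops study drug as it is. With follow-up maintained, Table JPBL.12.1 needs no new rule.

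Optionally, add a sentence that the discontinuation list does not end survival follow-up for patients who progress or enter another trial. This only makes explicit what Section 10.1.2 already implies.

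The cost is a wording change, plus follow-up contacts about every 12 weeks, and scans until progression, for a few patients. These visits are already in the schedule.

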7.3.2. Discontinuation of Study Sites

Study site participation may be discontinued if Lilly, the investigator, or the ethical review board (ERB) of the study site judges it necessary for medical, safety, regulatory, ethical, or other reasons consistent with applicable laws, regulations, and GCP.

[figure not shown]
7.3.3. Discontinuation of the Study

The study will be discontinued if Lilly judges it necessary for medical, safety, regulatory, ethical, or other reasons consistent with applicable laws, regulations, and GCP.

8. Investigational Plan

8.1. Summary of Study Design

Study I3Y-MC-JPBL (JPBL) is a multicenter, randomized, double-blind, Phase 3 trial for women with HR+, HER2- locally advanced or metastatic breast cancer. [Figure JPBL.8.1](#) illustrates the study design.

Abbreviations: HR+ = hormone receptor positive; HER2- = human epidermal growth factor receptor 2 negative; N = number; PD = progressive disease.

Figure JPBL.8.1. Illustration of study design.

Approximately 630 EP patients will be randomized 2:1 between the 2 arms:

- Experimental Arm A: abemaciclib 150 mg orally Q12H on Days 1 to 28 of a 28-day cycle plus fulvestrant 500 mg intramuscularly on Days 1 and 15 of Cycle 1, then on Day 1 of Cycle 2 and beyond
- Control (Placebo) Arm B: Placebo orally Q12H on Days 1 to 28 of a 28-day cycle plus fulvestrant 500 mg intramuscularly on Days 1 and 15 of Cycle 1, then on Day 1 of Cycle 2 and beyond

Enrollment will close when approximately 450 EP patients have been randomized at a starting dose of 150 mg Q12H. Patients will be randomized using the following stratification factors: nature of disease (visceral metastases versus bone only metastases versus other) and sensitivity to endocrine therapy (primary resistance versus secondary resistance). The presence of visceral metastases refers to lung, liver, pleural, or peritoneal involvement at the time of randomization. Primary clinical resistance to endocrine therapy is defined as follows: 1) for endocrine therapy in the adjuvant setting, recurrence within the first 2 years of adjuvant endocrine therapy while on endocrine therapy or 2) for endocrine therapy in the locally advanced or metastatic setting, progression within first 6 months of initiating first-line endocrine therapy while on endocrine therapy. Patients receiving prior endocrine therapy who do not meet the definition of primary clinical resistance will be considered to have secondary clinical resistance.

Data base lock for the interim analysis for efficacy will occur when approximately 265 investigator-assessed PFS events have been observed. Database lock for the final analysis of the PFS endpoint will occur when approximately 378 investigator-assessed PFS events have been observed. All patients will be followed for progression and survival information until death or study completion, whichever occurs first.

Details on sample size and analysis in Sections 12.1 and 12.2.

Terms used to describe the periods during the study are defined below:

- **Baseline:** begins when the informed consent form (ICF) is signed and ends at the first study treatment (or at discontinuation, if no treatment is given).
- **Study Period:** begins at the first study treatment and ends at study completion. The study period does not include the extension period.
 - **Study Treatment Period:** begins at the first study treatment and ends when the patient and the investigator agree that the patient will no longer continue study treatment. The date of this agreement is to be reported on the electronic case report form (eCRF) as the Date of Discontinuation from study treatment.
 - **Postdiscontinuation Follow-Up:** begins the day after the patient and the investigator agree that the patient will no longer continue study treatment.

Short-term follow-up begins the day after the patient and the investigator agree that the patient will no longer continue study treatment and lasts approximately 30 days.

[figure not shown]
Long-term follow-up begins the day after short-term follow-up is completed and continues until the patient's death or overall study completion.

- **Extension Period:** begins after study completion and ends at the end of trial. During the extension period, patients on study therapy who continue to experience clinical benefit may continue to receive study therapy until one of the criteria for discontinuation is met. The extension period includes extension period short-term follow-up.
 - Extension period short-term follow-up: begins the day after the patient and the investigator agree that the patient will no longer continue study treatment in the extension period and lasts approximately 30 days.

